
Objective Measures: (a) **Epigenetic (DNAm):** Peripheral blood specimens will be collected at baseline (gestation 12-22 weeks) and intervention week 12 (gestation of 24-34 weeks), as summarized in Table 1. The PD and/or RAs will arrange to meet participants to collect the blood and transport samples to the VCU School of Nursing's lab for DNA extraction.

Samples will be shipped to HudsonAlpha for DNA methylation assays. HudsonAlpha will use the following procedures for DNA methylation: genome-wide methylation patterns will be determined using the 450K HumanMethylation Chip (Illumina) according to the vendor's protocol. Briefly, DNA will be extracted from the blood samples using standard techniques (Puregene Isolation Kit; Qiagen). Following bisulfite conversion of the DNA, the methylation patterns of the 485,764 targets (including CpG islands, shores, open sea) interrogated in the 450K array will be determined. To verify the results of the 450K array for targeted regions of interest, single loci methylation-sensitive studies of bisulfite converted DNA will be conducted using standard methods.²⁰⁵ Gene-specific patterns of candidate genes chosen a priori will be closely examined. All samples will be coded prior to deliver to the testing labs. As methylation patterns vary from tissue to tissue, one concern is if the patterns present in white blood cells are reflective of the relevant cumulative epigenetic changes

involved in chronic depressive symptoms. Skepticism regarding the utility of blood for the assessment of conditions having brain/nervous system components has recently been diminished by the observation that comparable DNAm changes induced by environmental/social events occur in multiple tissues.⁷⁵ Based on these findings, Szyf²⁰⁶ noted that the results of recent investigations demonstrate that it is feasible to study behaviorally related DNA methylation signatures in peripheral cells²⁰⁶ (p.334). Given this supporting data, as well as the practical need to collect a minimally invasive specimen for study in this pregnant population, peripheral blood will be used to assess DNAm patterns. (b) Birth weight: At the postpartum visit, mothers will be asked to report the baby²⁰⁶s birth weight.

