Comparison Group Data: Archival data from an existing IRB-approved study (NIMHD2P60MD002256, PI: [name]) includes pregnant women recruited from the VCUHS and area clinics who did not receive the MOMS intervention yet were followed throughout their pregnancies and into the postpartum period, using psychobehavioral, birth weight, and DNAm measures identical to those proposed in this study. The de-identified data will be used to form two age/race-matched comparison groups: (a) positive comparison group (n=40): pregnant women with clinically relevant depressive symptoms receiving the UC; and, (b) negative comparison group (n=40): pregnant women without clinical depressive symptoms. The timelines of these studies align well; as of May 2015, the study has enrolled approximately 135 women (50% AA) with ~15% of the sample endorsing depressive symptoms (unpublished data). Data collection from the total expected sample (n=220) will be completed by early 2017, at which point the proposed study will be ready to derive the comparison groups for analysis. To facilitate longitudinal comparisons across the two studies, the pre-/post-intervention data for the proposed study will correspond to data collected early in the second trimester of pregnancy (approximately 12-22 weeks gestation) and late in second trimester/ early in third trimester of pregnancy (approximately 24-34 weeks gestation) respectively, in the comparison study, represented in Figure 2.

Data Analysis Plan

Aim 1: Evaluate the feasibility and acceptability of the MOMS intervention for chronic depressive symptoms during pregnancy: (a) Data related to recruitment, retention and adherence to the MOMS intervention will be analyzed using descriptive techniques, including percentages and means. The number of participants who complete each time point will be recorded and percentages of the following calculated: persons eligible to participate; persons who signed a consent form; and PA sessions attended, home PA participation, and participant attrition. Reasons for attrition will be described.

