Aim 3: Identify DNA methylation patterns associated with chronic depressive symptoms during pregnancy and investigate whether participation in the MOMS intervention targets these patterns: Drs. [name] and [name] will work closely and collaboratively to utilize statistical methods appropriate for this aim. Output from the 450K DNA methylation platform will be screened for process errors to ensure that the resultant data pass quality control standards (based on known sites having constant methylation, including genes influenced by X-inactivation) and then processed using the minfi Bioconductor package in the R programming environment.²¹⁰ While there is yet no established standard for the analysis of data from this platform, best practice recommendations have been published and will be followed.²¹¹⁻²¹⁴ CpG sites having a false discovery rate (FDR) <0.05 will be considered significant after multiple test correction. Sites recognized as differentially methylated will be evaluated using a suite of bioinformatic tools, such as the DAVID Functional Classification software program, to identify biological systems and/or functions that are consistently altered. Specifically, we will: (a) confirm genome-wide DNAm pattern differences between the non-intervention archival comparison groups: positive comparison (n=40) and negative comparison (n=40) over time (4 time points), using growth modeling methods; (b) identify within-group genome-wide DNAm pattern differences over time (pre/post the intervention) using paired t-tests (n=40); and (c) identify overlapping DNAm differences among the three groups (n=120) and prioritize CpG sites to further evaluate based upon specific candidate genes that have received attention in the literature in relation to depressive symptoms and mindfulness-based interventions, including: glucocorticoid receptor (GR) Nr3c1, its promoter region NGFI-A, and GR chaperone protein FKBP5;^{84,86-88} brain-derived neurotrophin factor (BDNF) and its receptor TrkB;⁸⁹⁻⁹² and estrogen receptor-alpha and related genes HP1BP3 and TTC9B.⁹³⁻⁹⁶ These steps are pictured in Figure 3.

The goal of these confirmatory and exploratory analyses is to determine whether DNA methylation patterns predict treatment response and whether the intervention has targeted DNA methylation differences identified in the steps outlined

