Blood samples will be collected by a trained phlebotomist (PD and/or RA). 8ml blood will be collected by venipuncture in 2 EDTA [purple top] tubes at two points in the study: study visit #1 and study visit #14. The PD and/or RAs will arrange to meet participants to collect the blood in a private, quiet location (most likely research space on the 4th floor of the VCU School of Nursing) and transport samples to the VCU School of Nursing's lab for DNA extraction. Samples will be shipped to HudsonAlpha for DNA methylation assays.

4. * Will Genetic Testing be conducted on any of the samples:

Yes

No

5. * Will any of the samples be used for a pregnancy test:

Yes

No

6. If yes, describe how positive pregnancy results will be communicated to the participant, particularly if minors are involved:

7. * Will any of the samples be used to screen or document alcohol or illicit drug use:

Yes

No

8. * I am aware that I may need to establish a research account with VCUHS Department of Pathology for specimen processing:

Yes

No

ID: MS8_HM20006941

[View: SF - Blood Details](#)

Blood Details

1. * Select all of the methods of sample collection that will be utilized in this study:

Individual Needle Stick(s)

Indwelling Catheter Placed Solely for This Study

Indwelling Catheter Placed for Other Reason(s)

Blood Collected at the Same Time as Non-Research Blood Collection(s)

Unused Blood Originally Drawn for Clinical Purposes

Other

ID: MS8_HM20006941

[View: SF - HIPAA](#)

HIPAA

1. * Describe the protected health information that will be obtained or used in this research:

Participants will self-report past and current medical history, current medications, pregnancy information (gestational age), depressive and other symptoms.

2. * Describe the source(s) of the protected health information:

participant self-report

3. * Explain how the PHI collected or used in this research is the minimum necessary to accomplish this research:

This is the minimum necessary for us to conduct the study and answer our research questions

4. * Select all pathways this research will employ to use or access PHI:

De-Identified Data (none of the 18 identifiers are recorded or associated with the research data)

Limited Data Set

Waiver of Authorization

Partial Waiver of Authorization

Signed Authorization Combined with Consent Form

Signed Authorization as Stand-Alone Form

Partial Waiver of Authorization

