1. * Select all types of recordings that will be made:

Audio

Video

Photographs

2. * Describe the purpose of the recordings, who will be recorded and when such recordings will occur:

Audiotapes from semi-structured interviews/transcribed interviews will be used for the qualitative (feasibility & acceptability) aim of the research study. The semi-structured interviews will be audiotaped and then transcribed by the RA and analyzed by the PI and research team. Audiotapes will be kept in a locked file in a locked office at the VCU SON until the data are transcribed into software on a password protected computer. All data collected by the research team are considered part of the participant's confidential record. Data collected from research participants will be kept in a locked file cabinet. All data will remain confidential. All data is stored on a secure server, and backed up daily. Patient identifying information will be stored in a separate database and will be password protected.

3. * Will participants or others be identifiable on the recordings or transcripts:

Yes

No

4. If yes, describe how the identities of individuals will be protected:

5. * Describe how recordings will be stored:

Audiotapes will be kept in a locked file in a locked office at the VCU SON until the data are transcribed into software on a password protected computer. Audiotapes will be destroyed according to VCU IRB process recommendations after the data are transcribed.

6. * Will the recordings be destroyed:

Yes

No

7. If yes, describe at what point and how recordings will be destroyed:

After the audiotapes are transcribed.

8. If no, explain why the recordings need to be maintained:

9. * Will the recordings be used outside of this research study:

Yes

No

Existing Data/Specimen Details

1. * Describe the source and nature of the data/specimens being obtained:

Archival data from an existing IRB-approved study (NIMHD2P60MD002256, PI: [name]) includes pregnant women recruited from the VCUHS and area clinics who did not receive the MOMS intervention yet were followed throughout their pregnancies and into the postpartum period, using psychobehavioral, birth weight, and DNA measures identical to those proposed in this study. The de-identified data will be used to form two age/race-matched comparison groups:

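### The plan does not describe the assay runs; if MOMS and archival methylation arrays were run separately, comparing their levels cannot separate group from run.

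*Combined protocol and SAP*

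**What the plan says.** All references are to the combined protocol and SAP.

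- **MOMS samples are new.** Research Description, item 4, Objective Measures: "Peripheral blood specimens will be collected at baseline (gestation 12-22 weeks) and intervention week 12 (gestation of 24-34 weeks". The same paragraph and item 3 of the sample-collection page give the route: "Samples will be shipped to HudsonAlpha for DNA methylation assays". The platform is the Illumina 450K chip, where "the methylation patterns of the 485,764 targets (including CpG islands, shores, open sea) interrogated in the 450K array will be determined".
- **The comparators are archival.** Comparison Group Data: "The de-identified data will be used to form two age/race-matched comparison groups". The source study is said to use "birth weight, and DNAm measures identical to those proposed in this study", and Existing Data/Specimen Details, item 1, says nearly the same. That form page could cover specimens, but its description is of data only.
- **Timing.** For the source study, "Data collection from the total expected sample (n=220) will be completed by early 2017". No laboratory, date or run is given for its arrays.
- **The comparison.** Specific Aim 3 says MOMS patterns will be compared with archival patterns. Data Analysis Plan, Aim 3, has three steps: (a) positive versus negative comparison groups within the archive; (b) paired pre/post t-tests within MOMS; and (c) to "identify overlapping DNAm differences among the three groups (n=120) and prioritize CpG sites to further evaluate".
- **Safeguards named.** These are a process-error screen, minfi processing, published best practice (not specified) and FDR <0.05. Objective Measures adds single-locus verification of targeted regions. No batch or study term, bridging sample or chip layout is mentioned.

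**The concern.** Array methylation values carry a contribution from the run in which they were produced. Sharing a platform and a measure does not mean sharing a run. If every MOMS sample sits in one set of runs and every comparator in another, a MOMS-versus-archive difference at a CpG site could come from the intervention, from the population or from the laboratory, and the data cannot say how much is laboratory.

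Step (b) has its own version of the problem. A woman's two samples are drawn about 12 weeks apart, and nothing requires them to be assayed together. If they are not, time is mixed with run.

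Aim 3 asks whether MOMS acts on depression-related methylation, and its results are meant to inform later work. A run artefact at this stage would be carried forward and could not be removed afterwards by analysis.

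**Working it through.** **Inputs from the documents.** Groups of 40 + 40 + 40 = 120, which reproduces the stated Aim 3 total (Study Population, item 3). 485,764 targets. FDR <0.05. Attrition of 20-40% (Study Population, item 3). Aim 3 has no power calculation to reproduce.

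**Assumptions, not in the documents.** A run offset of 0.1 to 1.0 SD at affected sites, 5% to 50% of sites affected, sites independent, and no true group difference.

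**1. Aliasing, if runs are separate.** Use columns (intercept, positive, negative, MOMS run). The row types are:

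- MOMS: (1, 0, 0, 1)
- positive: (1, 1, 0, 0)
- negative: (1, 0, 1, 0)

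Then run = intercept - positive - negative. The matrix has 4 columns and rank 3, so group and run effects are not separately estimable. This needs no assumption about the size of the offset. Adding one archival sample re-assayed in the MOMS run, row (1, 1, 0, 1), gives rank 4. The effects are then estimable, but precision depends on how many such samples there are.

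**2. Per-site false positives for levels.** Two-sided t-test at 0.05, noncentrality = d / sqrt(1/n1 + 1/n2). For 40 v 40 with d = 0.5: 0.5 x sqrt(20) = 2.24.

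| Offset d (SD) | MOMS v positive (40 v 40) | MOMS v both archival groups (40 v 80) |
|---|---|---|
| 0.1 | 0.073 | 0.081 |
| 0.25 | 0.197 | 0.249 |
| 0.5 | 0.598 | 0.726 |
| 1.0 | 0.993 | 0.999 |

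**3. Sites declared under the plan's own criterion.** Benjamini-Hochberg at 0.05, 485,764 sites, 40 v 40, mean of three simulations, no intervention effect:

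| Sites affected | 0.25 SD | 0.5 SD | 1.0 SD |
|---|---|---|---|
| 5% | 0 | 974 | 22,973 |
| 10% | 1 | 4,551 | 47,748 |
| 30% | 16 | 34,657 | 147,234 |
| 50% | 82 | 81,237 | 245,260 |

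FDR control does not help, because a run difference is a real difference between the two data sets.

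**4. Step (b), if pre and post are run apart.** Paired t-test, noncentrality = d x sqrt(n), with d in SDs of the difference. Attrition of 20% leaves 40 x 0.8 = 32 pairs; 40% leaves 40 x 0.6 = 24. For d = 0.3: 0.3 x sqrt(32) = 1.70 gives 38%, and 0.3 x sqrt(24) = 1.47 gives 29%, against a nominal 5%. For d = 0.1 the rates are about 9% and 8%.

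**5. Change instead of level.** Write the run offset as m in MOMS and a in the archive. A level comparison is biased by m - a. In a comparison of change, MOMS contributes (post + m) - (pre + m), so m cancels, and likewise a, provided each woman's samples shared a run. Simulation (4,000 runs, 40 v 40, offset 0.5 SD, within-woman correlation 0.5) gives type I error of 0.049 for change and 0.595 for level. If an archival woman's time points were in different runs with offsets a1 and a2, a bias of -(a2 - a1) remains in the comparison.

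**The case against.** **Separate runs are not stated.** A reader might infer from the archival label that the comparators were assayed earlier and elsewhere. The documents do not say so. The studies are close in time: archival collection ends in early 2017, and the DSMB letter to start this study is dated August 2016. The archive's PI is a co-investigator here. Joint assay is possible, and one sentence confirming it would close the between-study part. This objection stands, so the aliasing is conditional.

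**Step (c) may not compare levels.** It follows (a) and (b) and speaks of overlap, so it may only intersect their site lists. A constant between-study offset would then not enter. Figure 3, which pictures the steps, is not available here. This stands as a possible reading. Against it, the step is written as differences among three groups with n=120, and Specific Aim 3 says MOMS patterns will be compared with archival ones.

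**Shipping as collected is not stated either.** VCU Site Details says blood is stored and processed at the School of Nursing laboratory, which is compatible with batched shipment. What is missing is a requirement to assay pairs together.

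**The consequence may be negligible.** At 0.25 SD with 10% of sites affected, about one site passes FDR. This stands: no document supports any particular offset, and a reader should not infer that thousands of false sites are expected.

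**Mitigations exist.** Single-locus verification is planned, but it breaks the alias only if MOMS and archival DNA are tested together. Existing Data/Specimen Details, item 1, admits the lack of a concurrent randomised control as a validity threat, without mentioning assay run. Aim 3 is a preliminary aim in a feasibility pilot, which limits the severity but does not remove the problem.

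**Conclusion.** The concern holds conditionally. The documents establish that MOMS samples are newly assayed, that the comparators enter as archival data, and that no joint assay, bridging or shared run is planned. If the archival arrays were run separately, any MOMS-versus-archive comparison of levels is fully aliased with run. That result is structural and does not rest on an assumed offset. Minfi, unspecified best practice and FDR <0.05 cannot repair it.

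The size is unknown. Under the assumed offsets it runs from negligible to severe: about 7% to 99% per-site false positives at nominal 0.05, and about 1 to 47,700 sites under FDR <0.05 with 10% of sites affected, for offsets of 0.25 to 1.0 SD.

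Step (a) lies within the archive and is not aliased with study. Step (b) is affected only if a woman's two samples are run apart, which nothing prevents. The sponsor should make the change, in proportion to a secondary aim of a pilot.

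**What to change.** 1. **Objective Measures, and sample-collection item 3.** Hold extracted DNA and assay both samples from each MOMS woman on the same chip in the same run, with chip position randomised.
2. **Data Analysis Plan, Aim 3.** Define step (c) as the overlap of sites from (a) and (b), a between-group comparison of within-woman change, or both. State that MOMS-versus-archival level differences will not be interpreted as intervention effects unless archival DNA is interleaved or bridged on the MOMS chips.
3. **Before using archival change.** State the archive's laboratory, dates and runs, and check from its run records that each woman's time points shared a run. If they did not, report the cross-study comparison as confounded with run.

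Cost: the number of MOMS arrays is unchanged, and bridging or re-assay of archival DNA, if chosen, adds arrays. Methylation results come later, after the last week-12 draw. The archive's run records must be obtained, with raw intensity files if they are available.

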2. Examine the preliminary effects of the MOMP intervention on measures of maternal psychobehavioral factors (i.e., depressive symptoms, anxiety, ruminations, PA self-efficacy, attachment) at baseline, midpoint and end of the 12-week intervention, and at 6-weeks postpartum and at 10-20 months postpartum, and on baby♦'s birth weight, compared with archival data from depressed women receiving the UC, to estimate effect sizes to inform future studies.
3. Identify DNA methylation (DNAm) patterns associated with chronic depressive symptoms during pregnancy and investigate whether participation in the MOMP intervention targets these patterns: This aim will be accomplished by evaluating both genome-wide and gene-specific DNAm patterns (e.g., candidate genes putatively related to depression, pregnancy, and mindful interventions: Nr3c1, NGFI-A, FKBP5, BDNF, TrkB, HP1BP3, TTC9B). These patterns will be compared with patterns in recently collected archival data from pregnant women with and without depressive symptoms receiving UC.

3. * Describe the study's background and significance, including citations, or upload a citation list in document upload. Use lay language whenever possible.

Chronic and recurrent depressive symptoms are a significant public health problem.¹ Women with chronic depressive symptoms face significant treatment challenges during pregnancy. Close to 20% of women experience clinically significant depressive symptoms during pregnancy (e.g., feelings of sadness, anhedonia, sleep alterations, and fatigue, among others),² with the majority manifesting a recurrence of symptoms rather than a new onset.³⁻⁵ Although there are numerous pharmacological treatments available for depressive symptoms, data are conflicting with respect to safety of antidepressant medications during pregnancy and there is little research addressing efficacy of non-pharmacological therapies in this population.^{3,6,7} Currently, no therapies are universally effective at decreasing depressive symptoms and uniformly accepted as low obstetrical and fetal risk.^{8,9} Further, many pregnant women are concerned about stigma, side effects, fetal effects, and/or costs of the ♦usual care♦ (UC: antidepressants, psychotherapy) for symptoms and elect to avoid or decrease UC during pregnancy.¹⁰⁻¹⁶ Hence, many women with depressive symptoms remain un- or under-treated.³

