This pilot study is intended to provide effect size estimates to inform future studies, rather than having sufficient power to address intervention effectiveness. With regards to Specific Aim 2, the proposed sample size is expected to yield reasonably stable preliminary data, based on van Belle's assertion that a minimum of 12 observations should be used to calculate confidence intervals based on the t-statistic with $n - 1$ degrees of freedom. This rule is based on the fact that the half-width confidence interval for the mean decreases rapidly up to $n = 12$, at which point the decrease is less dramatic and the half-width curve begins to asymptotically decrease.¹⁷¹ Our previous experience with individuals with depressive symptoms in research studies has yielded attrition rates between 20-40%, hence our target sample size of 40 women to participate in the intervention will be sufficient to estimate group means and variances as well as within subject correlations to estimate effect sizes to guide the design of future studies. With regards to Specific Aim 3, the total sample size is $N=120$, which includes the intervention group ($n=40$), the positive comparison group ($n=40$), and the negative comparison group ($n=40$). This sample size is very appropriate, given that it is of greater magnitude to other related epigenetic studies. For example, Guintivano and colleagues identified DNA methylation patterns which successfully predicted the onset of postpartum depression in $n=93$ pregnant women;¹⁷⁰ Yehuda and colleagues identified DNA methylation differences between responders and non-responders to a psychological intervention in combat veterans with post-traumatic stress disorder in a sample size of $n=16.77$.

4. * List the study inclusion criteria:

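### Aim 3 judges whether MOMS targets depression-related CpG sites by overlap with a genome-wide FDR list, which loses much power when the change is concentrated at those sites

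*Combined protocol and SAP*

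**What the plan says.** Specific Aim 3 (Research Description, item 2) is to find methylation patterns linked to depressive symptoms and to "investigate whether participation in the MOMP intervention targets these patterns". The Data Analysis Plan for Aim 3 (Research Description, item 4) gives one significance rule, placed before the steps: "CpG sites having a false discovery rate (FDR) <0.05 will be considered significant after multiple test correction". The steps are:

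- Step (a), archival women only: "confirm genome-wide DNAm pattern differences between the non-intervention archival comparison groups", 40 against 40, by growth models.
- Step (b), MOMS women only: "identify within-group genome-wide DNAm pattern differences over time (pre/post the intervention) using paired t-tests (n=40").
- Step (c): "identify overlapping DNAm differences among the three groups (n=120) and prioritize CpG sites to further evaluate", with candidate genes guiding the priority.

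The closing goal is to learn "whether the intervention has targeted DNA methylation differences identified in the steps outlined" in the plan. On the size of the array, the Objective Measures section says "the methylation patterns of the 485,764 targets (including CpG islands, shores, open sea) interrogated in the 450K array will be determined". No section restricts the MOMS test, or its multiplicity correction, to the step (a) sites. Figure 3, which illustrates the steps, is not shown in the available text.

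**The concern.** The question is conditional: given the sites that differ by depression in the archive, does methylation at those sites change in MOMS women? The family that matches it is the step (a) list. Step (b) tests the whole array under FDR <0.05, and step (c) then looks for overlap.

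Benjamini-Hochberg (BH) sets its cut-off from the number of small p-values in the whole family. A depression site is therefore judged against a threshold that depends on how many unrelated sites move. If MOMS acts mainly at the depression sites, which is what targeting would mean, few other sites move, the threshold is extreme and real changes are missed. A sparse or empty overlap could then be taken as evidence against targeting when it mostly reflects the choice of family. In addition, a 5% FDR over the array does not formally carry over to a subset or to the intersection of two lists.

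**Working it through.** **Inputs from the documents.** 485,764 sites (Objective Measures); FDR 0.05, paired t-tests and n=40 (Aim 3 plan). On attrition, the sample-size justification (Study Population, item 3) says "Our previous experience with individuals with depressive symptoms in research studies has yielded attrition rates between 20-40" percent, so 40 × 0.80 = 32 or 40 × 0.60 = 24 pairs. The stated Aim 3 total reproduces: 3 × 40 = 120. No power, effect size or expected number of step (a) sites is given for Aim 3, so there is no power figure to reproduce.

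**Assumptions, not in the documents.** 200 step (a) sites, 50 of them shifted by 0.7 SD of the paired difference; 0 or 5,000 other sites shifted equally; two-sided tests; independent sites.

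**Formula.** BH over N tests rejects all p ≤ t, where approximately t = 0.05 × R(t)/N and R(t) is the expected number of p-values at or below t, that is (null sites × t) + (shifted sites × power at t).

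**Worked case, 40 pairs.**

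- Whole array, nothing else moves: t = 5.74e-7. Check: 485,714 × 5.74e-7 + 50 × 0.106 = 0.28 + 5.30 = 5.58, and 0.05 × 5.58/485,764 = 5.74e-7. Power is about 11%.
- Whole array, 5,000 others move: t = 3.81e-4. Check: 480,714 × 3.81e-4 + 5,050 × 0.697 = 183 + 3,520 = 3,703, and 0.05 × 3,703/485,764 = 3.81e-4. Power is about 70%.
- Within the 200 sites, whatever happens elsewhere: t = 0.0125. Check: 150 × 0.0125 + 50 × 0.960 = 1.9 + 48.0 = 49.9, and 0.05 × 49.9/200 = 0.0125. Power is about 96%.

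**Simulation with the same assumptions** (ranges are across repeat runs). Share of the 50 true sites found:

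| Pairs | Others moving | Genome-wide BH, then overlap | BH within the 200 |
|---|---|---|---|
| 24 | 0 | 0.1–0.2% | 74% |
| 32 | 0 | 3% | 88–90% |
| 40 | 0 | 8–11% | 96% |
| 24 | 5,000 | 13–15% | 70–71% |
| 32 | 5,000 | 44–46% | 89–90% |
| 40 | 5,000 | 68–70% | 96–97% |

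**Other inputs.** With 100 step (a) sites, 20 of them shifted by 0.8 SD, and 40 pairs, the overlap finds 23%, 86% and 99% as 0, 5,000 and 50,000 other sites move. Within-family BH finds 98–100% throughout. With 24 pairs the figures are 1%, 32% and 77%, against 85–87%.

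**Single-rejection threshold.** This comparison needs no assumed number of shifted sites. The strictest BH cut-off is 0.05/485,764 = 1.03e-7 for the array. The smallest paired shift detected with 80% power at that cut-off is 1.19 SD with 40 pairs and 1.79 SD with 24. For a family of 100 sites it is 0.74 and 1.02 SD.

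**Error side, 32 pairs, other sites shifted by 0.8 SD.**

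- None of the 200 step (a) sites moves: the chance of at least one false overlap is 0% with no others moving, 6–8% with 5,000, 33–48% with 25,000 and 59–64% with 50,000. The last agrees with 1 − (1 − 0.005)^200 = 63%. Within-family BH gives 1–8%, around its nominal 5%.
- Step (a) sites move at the array-wide rate: 200 × 25,000/485,764 = 10.3 sites, or 20.6 for 50,000. FDR in the overlap is 4.2% and 4.1%, against 4.2% and 4.4% within the family. Power is 86% against 86%, and 93% against 93%.
- Intermediate case, 40 pairs: 25 of 500 step (a) sites move (5%). Overlap FDR is 9% when 50,000 others move (10.3% of the array) and 22% when 150,000 move (30.9%).

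**The case against.** **The intersection rule is inferred.** The text does not say that a site must pass FDR in both (a) and (b); the FDR sentence names no family, and Figure 3 might say more. This stands as a caveat. A reader should not infer that the plan explicitly prescribes a list intersection. But the text gives no other rule, and naming the family settles the matter on any reading.

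**The error rate is not badly broken.** A reader might infer from the 59–64% figure that the overlap list would be full of chance findings. That scenario needs tens of thousands of sites to move while none of the step (a) sites do. Gestational change, the obvious cause of widespread movement, has no reason to spare them. When they move at the array-wide rate the two rules behave alike. This objection largely succeeds; what remains is that the 5% is not guaranteed for the overlap.

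**Candidate genes offer another route.** The plan will examine pre-chosen genes closely, so the overlap is not the only path to a conclusion. However, no test or error family is given for them, and they are not the step (a) list.

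**This is a pilot.** Feasibility is the primary aim, and the sample-size section disclaims power for effectiveness. That lowers the priority. The targeting question is still asked, under a 5% rule, and with perhaps 24 to 32 pairs there is little power to give away.

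**The remedy is conditional too.** BH within the step (a) list does not cover false entries on that list. This is correct and must be stated.

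**Conclusion.** The point holds as one about power and an unspecified family. On the natural reading, the plan tests the depression sites at a threshold set by unrelated sites, and this costs most in the situation that Aim 3 is looking for. Under the assumptions above, about 0–10% of true sites are found against 74–96% when nothing else moves, and about 14–70% against 70–97% when 5,000 other sites also move.

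The mechanism does not depend on the assumed inputs; the size does. The number of step (a) sites, the effect size, the number of other sites moving and independence between sites are all assumed.

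Two stronger conclusions are not supported. One is that a real effect would almost never be found: with 40 pairs, 0.8 SD and nothing else moving, the overlap still finds 23%, and far more if other sites move. The other is that false overlaps are a general problem: they need the step (a) sites to be largely spared. The change is worth making, but it does not undermine the pilot's primary aim.

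**What to change.** Rewrite step (c) as a two-stage test:

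1. Take the CpG sites passing FDR <0.05 in step (a) as a closed family, fixed before MOMS change is examined.
2. Test MOMS pre/post change at those sites only, with BH at 0.05 within the family, and base any statement about targeting on this result.
3. Keep the genome-wide step (b) scan as a separately labelled exploratory list.
4. If step (a) yields no site, state that the targeting question cannot be answered.

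Step (a) uses archival women only and step (b) MOMS women only, so choosing sites in (a) does not bias the MOMS p-values.

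Add two statements. First, the 5% applies to MOMS change conditional on the step (a) list and does not cover false step (a) sites, which may average up to 5% of that list. Second, this change does not separate a MOMS effect from gestational change, because step (b) remains a within-group comparison.

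The cost is a few sentences and a line or so of code, with no new data or assays. There is a small downside if a very large share of the array changes. With 24 pairs, 25 of 500 step (a) sites shifted by 0.8 SD and 50,000 others moving, the restricted test finds 68% of true sites against 79% for the overlap (FDR 4% against 7%). With 150,000 moving it is 68% against 89% (FDR 3.5% against 23.5%).
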